## 1 Protocol Summary

Study Title	Prostatic Urethral Lift in Subjects with Acute Urinary Retention Study (PULSAR)
Study Objectives	Assess feasibility and safety of the Prostatic Urethra Lift (PUL) procedure in patients with acute urinary retention secondary to BPH. Research methodology will also be evaluated for larger, randomised study.
Study Design	Multi-centre, prospective evaluation of PUL and retrospective review of invasive surgery as potential comparator.
Sample Size	Up to 55 subjects treated with PUL. Retrospective chart review will include BPH patients that presented with AR and went on to de novo invasive surgery from June 1, 2015 to December 31, 2015.
Subject Population	Males over the age of 50 diagnosed with symptomatic benign prostatic hyperplasia (BPH) and ongoing acute urinary retention after failed TWOC.
Number of Centres (Sites)	Up to six centres in the United Kingdom.
Clinical Indication	The UroLift System is indicated for the treatment of symptoms due to urinary outflow obstruction secondary to benign prostatic hyperplasia (BPH) in men 50 years of age or older.
Primary Study Assessment	Successful post-procedure voiding trial without catheter (2-4 days).
Safety Assessment	Rate of serious adverse events (SAEs) related to BPH intervention through 3 months.
Additional Assessments	1. Need for further clean intermittent self-catheterisation (CISC) 2. Urinary symptoms, post void residual (PVR) and peak flow rate over follow-up 3. Subjects free from urinary retention through 1 month, 6 weeks, 3, 6 and 12 months 4. Subjects free from alternative surgical procedure for BPH through 12 months 5. Duration of catheter prior to treatment and in follow-up between prospective (PUL) and retrospective (TURP/HoLEP) 6. Rate of AEs in prospective PUL and retrospective TURP/HoLEP 7. Assess enrolment rate, willingness of patients to enrol, inclusion criteria, and appropriateness of endpoint
Follow-up Evaluations	Post-procedure, 6 weeks, 3 months, 6 months (remote), 12 months
Anticipated Study Duration	
First patient in (FPI)	15-April-2018
Last patient in (LPI)	31-December-2018
Endpoint analysis	28-February-2019
Study close	01-April-2020

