**Table 2 Definitions**

Adverse event (AE)	An adverse event (AE) is defined as any undesirable medical occurrence in a clinical trial subject, whether it is considered to be related to the device or not, that includes a clinical sign, symptom, or condition.  Once a subject is enroled, all AEs must be reported through follow-up period. Only exacerbated conditions or new onset qualify as an AE. Principal Investigator will assess severity, relatedness, serious or unexpected.
Alternative Surgical Intervention	A post-index procedure surgery, other than PUL, to treat BPH.
Acute Urinary Retention	Painful inability to void and a residual volume < 1500 mL.
Invasive BPH surgery	
 
• Transurethral resection of the prostate (TURP)
 
• Transurethral Laser (PVP, HoLEP or Interstitial)
 
• Open Prostatectomy
 

Index procedure	The first procedure to which subjects are enroled.
Precipitated AR	Acute urinary retention that develops in response to a trigger such as UTI, anaesthesia, surgery, medications with sympathomimetic or anticholinergic effects.
Serious Adverse Event (SAE)	
Serious Adverse Event (SAE) is defined as untoward occurrence that: (a) results in death; (b) is life-threatening; (c) requires hospitalisation or prolongation of existing hospitalisation (d) results in persistent or significant disability or incapacity; (e) consists of a congenital anomaly or birth defect; or (f) is otherwise considered medically significant by the investigator.
 
(in-patient hospitalisation is at least 24 consecutive hours)

Unexpected Adverse Event	An unexpected adverse event is an event which by nature, incidence, severity or outcome has not been identified in the current version of the Sponsor risk management files.
Spontaneous AR	Associated with older age, BPH, elevated PSA, or presence of severe LUTS.
PUL Procedure Time	Time from first device insertion to last device removed.

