### 8.1 Inclusion Criteria

---

Subjects enroled in this clinical study must meet all of the following criteria.

1. Male gender
2. Diagnosis of symptomatic BPH
3. Age  $\geq$  50 years
4. Prostate volume  $\leq$  100 cc per ultrasound (US)
5. Acute urinary retention with at least one failed trial without catheter (TWOC) while on alpha blocker

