## 15.3 Modified Enrolment Criteria for Retrospective Arm

### 15.3.1 Retrospective Inclusion Criteria

Patients enroled in this study must meet the following criteria:

1. Male gender
2. Diagnosis of symptomatic BPH
3. Age  $\geq$  50 years
4. Presented with acute urinary retention with at least one failed trial without catheter prior to invasive surgery (index procedure)
5. Underwent invasive BPH surgery (TURP, HoLEP, etc.) while in retention and performed by site between June 01, 2015 and December 31, 2015.
6. Prostate volume  $\leq$  100 cc as measured by ultrasound, specimen (tissue) weight, or other standard method for prostate evaluation

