## 16 Study Data Analysis

---

All effectiveness analyses will be performed on the “intent-to-treat (ITT)” group. All subjects who were enroled with at least one UroLift device introduced will be included in the intention to treat analysis. Effectiveness assessments for enroled subjects whom later undergo surgical retreatment with either PUL or with any other surgical procedure will be censored the day after the secondary intervention. Censoring in adverse event analysis will be applied only to alternative surgical retreatments and not to secondary PUL.

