### 16.3 Safety Population

---

The safety population will be used for all safety assessments. The safety population includes all enroled subjects with at least one UroLift device introduced. Safety assessments for enroled subjects whom later undergo surgical retreatment with any other surgical procedure will be censored on the day of the secondary intervention. Censoring in adverse event analysis will be applied only to alternative surgical retreatments and not to secondary PUL.

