## 16.6 Additional Assessments

---

Continuous measures will be summarised by visit. Summary statistics will include the available sample size, mean and standard deviation. Changes from baseline to each follow-up visit will also be calculated and the summary statistics will include the number of patients with change score available, mean, median, standard deviation, and confidence intervals (CI). These assessments will be calculated for both the ITT and PP analysis populations.

The Kaplan-Meier method will be used to calculate freedom from alternative secondary surgery over time and freedom from medical treatment, from the time of the PUL procedure for the ITT and PP populations. Subjects that do not have an alternative procedure will be censored at their last recorded follow-up visit. The probability of freedom from urinary retention will be analysed in a similar manner for the safety population. Time without catheter will be analysed using the Kaplan-Meier method in the ITT and PP populations.

Adverse events will be summarised by overall adverse events (AEs), severe AEs (grade 3 or higher on CTCAE scale), AEs related to device and/or procedure, serious adverse events (SAEs) and SAEs related to device and/or procedure. Adverse events will be coded using MedDRA and CTCAE v4.0 severity grades and will be presented by System Organ Class (SOC) and preferred term. Adverse events will be summarised for the safety population.

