### **Retrospective Arm**

The following baseline and procedural data points will be summarised for both the retrospective and the prospective arms. Although the study is not powered to make comparisons between the retrospective surgical patients and the prospective Urolift subjects, comparisons in the observed data will be made statistically. Continuous variables will be compared using a t-test or non-parametric alternative, binary data points will be compared using chi-square or Fisher's exact test.

- 1) Baseline demographics

- 2) Duration of catheterisation to procedure (days)
- 3) Procedure time
- 4) Hospitalisation time

The following outcomes post procedure will be summarised for the retrospective surgical group and will compared to the results obtained in the prospective study. The statistical significance of any observed differences will be assessed.

- 1) Total numbers of related AE, SAE, and Clavien-Dindo  $\geq$ IIb individually
- 2) Percent procedure/device related AE rates by month post index procedure and by severity
- 3) Retreatment post index intervention by time to event and by month
- 4) Medical treatment post index intervention by time to event and by month
- 5) Urinary retention recurrence rates at 1 month, 6 weeks and at 3, 6 and 12 months
- 6) Post-procedure TWOC success percent
- 7) Catheterisation use

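### The arms are compared on retention recurrence although every man enters in retention, so a man whose retention never resolves has no defined place in the result

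*Combined protocol and SAP*

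**What the plan says.** **Entry state.** Prospective inclusion criterion 5 (Section 8.1) requires "Acute urinary retention with at least one failed trial without catheter (TWOC) while on alpha blocker". Retrospective inclusion criterion 5 (Section 15.3.1) requires that the man "Underwent invasive BPH surgery (TURP, HoLEP, etc.) while in retention and performed by site" in the stated 2015 period. All men in both arms therefore start in retention.

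**The outcome has two names.** Among the post-procedure outcomes compared between arms (Section 16.6, Retrospective Arm), item 5 is "Urinary retention recurrence rates at 1 month, 6 weeks and at 3, 6 and 12 months". The Protocol Summary, additional assessment 3, lists "Subjects free from urinary retention through 1 month, 6 weeks, 3, 6 and 12 months".

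**Time-to-event analysis.** Section 16.6 runs Kaplan-Meier curves from the PUL procedure and adds: "The probability of freedom from urinary retention will be analysed in a similar manner for the safety population".

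**Censoring.** For the safety population, Section 16.3 says that assessments of men who later have a different surgical procedure "will be censored on the day of the secondary intervention". For effectiveness, the opening of Section 16 says that assessments of men who have "surgical retreatment with either PUL or with any other surgical procedure will be censored the day after the secondary intervention". Neither rule makes an exception for a man still in retention.

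**Definition.** Table 2 defines acute retention as "Painful inability to void and a residual volume < 1500 mL". It does not define recurrence, the start of the at-risk period, or the status of a man kept comfortable by an indwelling catheter.

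**The concern.** Recurrence, in its ordinary sense, presupposes resolution. A man who fails every TWOC after the procedure has nothing to recur. If the term is applied as written, persistent retention, which is the clearest failure of the treatment, adds to the denominator of item 5 and never to the numerator.

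The Kaplan-Meier curve has a related gap. It starts when every man has a catheter in place (Section 10.3.4 places one prophylactically), and no event is defined. If persistent retention is not treated as an event, the man stays at risk as retention-free until alternative surgery and is then censored. That censoring is informative, because Section 10.10.1 names recurring retention requiring a catheter as a reason for such surgery.

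Other rules leave little to fall back on within this outcome. Section 14.3 keeps reoccurring retention out of the adverse event data. Section 10.10.1 drops study visits other than month 12 once surgery is scheduled. Section 16.4 plans no imputation.

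At stake are the retention-durability estimate for PUL and its comparison with surgery, both of which Sections 6.1 and 16.7 intend to carry into the design of a larger trial.

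**Working it through.** The documents give no expected recurrence rate or precision target for this outcome, so there is no figure of the plan's own to reproduce. The check is first textual, then an illustration with assumed counts.

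**Step 1. One man followed through the plan.** Suppose he fails every TWOC after PUL and keeps his catheter until TURP at month 5.

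| Result | What the text gives for him |
|---|---|
| Item 5, recurrence | Read literally, no event at 1 month, 6 weeks or 3 months |
| Summary, free from retention | Read plainly, not free at any of those times |
| Kaplan-Meier, freedom from retention | Event not defined: either an early event, or censored at month 5 as retention-free |
| TWOC success, catheter use, retreatment, time without catheter | Shown as a failure |

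The first two rows disagree about the same man at the same time points, and the third depends on an unstated choice.

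**Step 2. Size in one arm.** Inputs: N = 55, the maximum in Section 7; 8 never-voiders and 5 men who void and later relapse, both assumed. Intervals are exact binomial, 95%.

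- Recurrence over all treated men: 5/55 = 9.1% (3.0% to 20.0%).
- Not free from retention: (8 + 5)/55 = 13/55 = 23.6% (13.2% to 37.0%).
- Recurrence among men who voided: 5/(55 − 8) = 5/47 = 10.6%.

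The gap between the first two is 8/55 = 14.5 points. It equals the share of never-voiders by construction, so it shows what drives the gap and does not predict its size.

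**Step 3. Effect on the Kaplan-Meier curve.** Assumptions: N = 55, alternative surgery for never-voiders at about day 120, about 10% of voiders relapsing during the year. The estimate is S(12 months) = product over event times of (1 − d/n).

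Example with 17 never-voiders and relapses on days 20, 95, 170 and 245:
- Never-voiders censored at surgery: (54/55)(53/54)(35/36)(34/35) = (53/55)(34/36) = 91.0%.
- Never-voiders counted as events at day 3: (38/55)(34/38) = 34/55 = 61.8%.

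| Never-voiders | Relapses | Censored at surgery | Event at day 3 |
|---|---|---|---|
| 6 | 5 | 90.2% | 80.0% |
| 11 | 4 | 91.8% | 72.7% |
| 17 | 4 | 91.0% | 61.8% |
| 22 | 3 | 93.3% | 54.5% |

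The choice moves the 12-month figure by about 10 to 39 points. With about 20% relapse, the pairs run from 80.4% versus 70.9% (6 never-voiders) to 81.9% versus 47.3% (22).

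**Step 4. Effect on the arm comparison.** Assumptions: 55 men per arm (the size of the surgical arm is not given) and about 10% relapse among voiders in each arm, which gives 4 recurrences with PUL and 5 with surgery in every row (Fisher p = 1.0).

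| Never-voiders, PUL vs surgery | Any retention failure | Fisher p |
|---|---|---|
| 11 vs 3 | 15 vs 8 | 0.16 |
| 17 vs 3 | 21 vs 8 | 0.009 |
| 11 vs 6 | 15 vs 11 | 0.50 |
| 17 vs 6 | 21 vs 11 | 0.058 |

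Recurrence shows no difference throughout, even where total retention failure differs widely.

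**The case against.** The strongest defence is that nothing in the protocol says a never-voider counts as free of retention. The Kaplan-Meier analysis and the Summary both use freedom from retention. On a plain reading, a man re-catheterised after a failed day-3 TWOC is not free, would be an event that day, and later censoring at TURP would change nothing. Item 5 does not say that its rates are Kaplan-Meier estimates, so the literal meaning of recurrence and the censoring rule belong to two different analyses. Measuring resolution by TWOC and recurrence afterwards is also a coherent pair, and the same list compares retreatment (item 3), TWOC success (item 6) and catheter use (item 7). The plan adds the 1-month catheter-free rate, time without catheter, a count of initial failures who later void (Section 6.4) and an adjudicated treatment failure (Section 10.11). Finally, the comparison is stated to be unpowered and there is no success criterion (Section 16.7).

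Most of this stands, and it limits the point. A reader might infer that the plan counts persistent retention as success throughout. It does not: the curve's event is open, and failure is visible in other results. A reader might also infer that reported durability improves steadily as more men fail outright. In Step 3 the censored curve is nearly flat, between 90.2% and 93.3%. Only the crude rate over all treated men falls, from 5/55 = 9.1% with 6 never-voiders to 3/55 = 5.5% with 22.

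What the defence does not answer is item 5 itself. Its literal meaning gives no event for a persistent failure, and nothing elsewhere overrides that. Day-3 TWOC cannot substitute, since Section 10.11 acknowledges that it does not address durability, and alone it cannot separate a man who voids at a second attempt from one who never does. Section 16 gives no analysis of adjudicated treatment failure.

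**Conclusion.** The point holds in a limited form. Followed literally, item 5 gives a misleading between-arm retention result, because both arms start in retention and a man whose retention never resolves has no recurrence. The Kaplan-Meier curve permits, but does not require, the same man to be censored as retention-free.

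The harm is confined to the recurrence and freedom-from-retention results. Its size is set by the share of never-voiders in each arm, which the documents do not give. The 9% versus 24% contrast rests wholly on the assumed 8 and 5 men, and Steps 3 and 4 rest on assumed relapse rates, surgery timing and arm sizes. In a feasibility study without a success criterion, the consequence is a distorted durability estimate carried into the next trial's design, not a wrong formal decision. It should be corrected before the arms are compared.

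**What to change.** 1. **Item 5.** Make the main comparison the proportion of all treated men not free from retention at each time point: retention that has not resolved since the index procedure, has returned, or has led to alternative surgery. Use the same term in the Summary and Section 16.6.
2. **Kaplan-Meier curve.** Count a man who never passes a post-procedure TWOC as an event dated at his first failed TWOC. Do not treat surgery for unresolved or returned retention as non-informative censoring.
3. **Late successes.** Men who fail the first TWOC and pass a later one are not persistent failures. Report them in the count already listed in Section 6.4. Making any first failure a lasting event would largely repeat the primary assessment. It would also label as failures for 12 months men who void at the repeat attempt that Section 10.4 requires.
4. **True recurrence.** Report it separately, only among men who passed a TWOC, with that denominator stated.
5. **Surgical charts.** Apply the same definitions where the data allow, and report how many men cannot be classified.

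The PUL data are already collected: Section 10.4 records all catheterisations, and repeat attempts are required. Section 15.8.3 collects surgical catheterisations only if available, so some charts will be unclassifiable. The cost is a small amendment to Section 16, with the approvals in Sections 17.6 and 22, one extra table, and a less favourable retention-free rate. No treatment or visit changes.

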## 6.2 Primary Study Assessment

---

The primary study assessment will be successful trial without catheter (TWOC). Success is defined as a spontaneous voided volume of  $\geq 100$  mL associated with a post void residual volume by ultrasound  $< 300$  mL at 3 days ( $\pm 1$  day) post index procedure.

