#### 10.4 Post-Procedure Trial Without Catheter (TWOC)

The subject will return to clinic **3 days ( $\pm 1$  day)** after Index procedure for the primary study assessment screening of bladder function without catheter. TWOC will be considered successful if the spontaneous void is  $\geq 100$  mL with PVR  $< 300$  mL. If subject fails the initial TWOC, at least one additional TWOC will be performed per standard of care. All catheterisations will be recorded on the eCRF.

The following evaluations will be performed in office **3 days ( $\pm 1$  day)** after index procedure in conjunction with the TWOC:

- Relevant Concomitant medications: BPH/LUTS; Sexual Function; GU; Prostate Cancer
- Freestanding uroflow and post void residual (PVR)
- Catheterisation review
- Adverse Event review; Intervention review

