## 15.8 Case Abstraction: Data Collection

### 15.8.1 Screening

The following medical history parameters will be collected from time when patient presented with AR.

 
• Inclusion/Exclusion confirmation
 
	
 
• Prostate volume (cc) by ultrasound or other methods
 
	
 
• History of BPH: length of time, symptom scores, treatments sought
 
	
 
• Catheterisation and TWOC history
 

 
• Co-morbidities
 
	
 
• Uroflowmetry/PVR within 6 months prior to intervention
 
	
 
• IPSS within 6 months prior to intervention
 
	
 
• Other GU treatments
 

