### 15.8.3 Post-procedure

The following post-surgery data will be collected for period after discharge through 12 months after their surgical intervention (if available):

• Date of contacts	• Type, reason of contact (phone, office visit)	• Complications, adverse events (urological, sexual function, cancer and SAEs)	• Interventions
• BPH medications, indication	• Symptom scores	• Uroflowmetry/PVR	• Catheterisations

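### Post-procedure TWOC success is to be tested between arms, but the protocol lists no data that let the surgical arm be scored on the PUL rule and time window

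*Combined protocol and SAP*

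**What the plan says.** All references are to the combined protocol and SAP.

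- **Between-arm analysis.** Section 16.6, Retrospective Arm, has two lists. Item 6 of the second (post-procedure outcomes) is "Post-procedure TWOC success percent". For that list the plan states: "The statistical significance of any observed differences will be assessed". The test is named with the first list: "binary data points will be compared using chi-square or Fisher's exact test". The same text concedes the limit: "Although the study is not powered to make comparisons between the retrospective surgical patients and the prospective Urolift subjects".
- **Rule in the PUL arm.** Section 6.2: "Success is defined as a spontaneous voided volume of" at least 100 mL, with PVR below 300 mL, at 3 days (±1 day) after the index procedure. Section 10.4, which governs the prospective cohort, repeats it: "TWOC will be considered successful if the spontaneous void is" at least 100 mL with PVR below 300 mL. It is applied at a scheduled clinic visit, after a catheter placed prophylactically (section 10.3.4).
- **Surgical arm, before surgery.** Section 15.8.1 collects "Catheterisation and TWOC history" as medical history from when the patient presented with retention.
- **Surgical arm, procedure.** Section 15.8.2 lists catheterisation and duration of hospital stay, if available. It has no TWOC, voided volume or PVR item.
- **Surgical arm, afterwards.** Section 15.8.3 opens: "The following post-surgery data will be collected for period after discharge through 12 months after their surgical intervention (if available". The list includes uroflowmetry/PVR and catheterisations, but no TWOC item and no visit window.

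**The concern.** A test of two proportions has a meaning only if success is the same event in both groups. Here one group is measured prospectively against two volume thresholds in a three-day window. The other would be read from notes, with no stated rule for what counts as success, which attempt counts, or on which day. A difference, or the absence of one, could come from the procedure or from how success was recorded, and the analysis cannot separate the two.

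The comparison has consequences even in a feasibility study. Section 6.1 makes comparison with surgical patients a study objective and says the study will help settle the endpoint for a larger trial. A p-value on this item would be read in that light.

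**Working it through.** The plan states no expected TWOC rate, alpha level or retrospective sample size, so there is no figure of its own to reproduce. The check is a comparison of the text, followed by an illustration.

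**Step 1: what the PUL rule needs, and what the surgical lists supply**

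| Needed to score TWOC success | PUL arm | Surgical arm, as listed in 15.8 |
|---|---|---|
| A TWOC after the procedure | Scheduled visit (10.4) | No item; TWOC is pre-operative history only (15.8.1) |
| Voided volume | Measured at that visit | Not named at the procedure stage; uroflowmetry after discharge, if available |
| PVR | Measured at that visit | Not named at the procedure stage; after discharge, if available |
| Timing | 3 days (±1 day), so days 2 to 4 | No window |
| Which attempt counts | The visit TWOC; repeats are handled separately (6.4, 10.4) | Not stated |

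A voiding trial held before discharge falls under 15.8.2, where only catheterisation is listed. Its volumes are not asked for. A uroflow after discharge may exist, but nothing ties it to days 2 to 4. No rule converts catheterisation or uroflowmetry/PVR into TWOC success. Section 16.4 plans no imputation, so the surgical denominator would be the charts that happen to hold a result.

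**Step 2: could a measurement difference alone produce a significant result?**

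Every input except the 55 PUL subjects (the maximum in the Protocol Summary) is an assumption: equal true success in both arms (70% or 80%), a retrospective N of 25, 55 or 100, and a two-sided Fisher exact test at 0.05. With success probability p in the PUL arm and p + s in the surgical arm, where s is due only to the rule used, the rejection probability is

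Σᵢ Σⱼ Bin(i; 55, p) · Bin(j; N, p + s) · 1[Fisher p-value < 0.05].

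| Retrospective N | p | s = 0 | s = 5 points | s = 10 points | s = 15 points |
|---|---|---|---|---|---|
| 25 | 70% | 3.7% | 5.1% | 11.1% | 23.6% |
| 25 | 80% | 3.3% | 4.3% | 10.8% | 27.8% |
| 55 | 70% | 3.1% | 6.0% | 16.8% | 38.4% |
| 55 | 80% | 2.7% | 6.3% | 21.9% | 57.0% |
| 100 | 70% | 4.2% | 9.0% | 25.7% | 54.8% |
| 100 | 80% | 4.0% | 10.4% | 36.1% | 78.5% |

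With a common rule the test stays below 5% (2.7% to 4.2%). A shift of 5 points has little effect (4.3% to 10.4%). A shift of 10 points gives 10.8% to 36.1%, and 15 points gives 23.6% to 78.5%. Only upward shifts were run. That choice is for illustration and is not evidence that chart-recorded success is more lenient.

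**The case against.** The case on the other side has five parts.

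1. **A rule for both arms may already exist.** Section 6.2 is not limited to PUL, and sections 15.3.1 and 15.3.2 also use the term index procedure for the surgery. This stands as a possible reading, so it would be too strong to say that no definition exists at all. But section 15 does not take the rule up, and its lists do not ask for the volumes at days 2 to 4. On this reading the surgical arm has a rule that the listed data cannot score.
2. **The eCRF may hold the fields.** Table 12 leaves exact data requirements to the EDC system and worksheets and speaks of consistency between arms. The eCRF is not in the documents, so the absence can be shown only for the protocol's own lists. Table 12 gives no TWOC rule, and it recommends defining outcome variables in advance.
3. **In-hospital catheter use is probably captured.** It is, through the catheterisation item in 15.8.2. A reader might infer that an early TWOC lies wholly outside the abstraction period, but the lists do not support that. What may be lost is the voided volume and PVR.
4. **Better comparisons are already planned.** Retention recurrence, including at 1 month (item 5), and catheterisation use (item 7) are compared between arms, and the 1-month catheter-free rate is an assessment in sections 6.4 and 16.5. This stands, and it makes item 6 easier to give up.
5. **The study is unpowered and has no formal success criteria (16.7).** This limits the weight of the result. It does not cure the problem, because low power gives no protection against a difference in measurement.

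**Conclusion.** The point holds in a limited form. As written, item 6 would test a protocol-measured outcome against an incompletely charted one, with no common rule or time window. This goes beyond wording, because the listed surgical data cannot supply what the PUL rule requires.

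Two stronger readings are tempting and are not supported:

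- **That the primary assessment is compromised.** It is the PUL success percentage at the 3-day visit in the ITT and PP populations (section 16.5), and it uses no surgical data.
- **That the bias runs against PUL by a known amount.** Suppose 85% clinician-declared success in both arms, with 10% to 20% of those successes failing the volume rule. PUL would then read 0.85 × 0.90 = 76.5% down to 0.85 × 0.80 = 68.0%, a gap of 8.5 to 17 points. Both inputs are invented, and a stricter local criterion would reverse the sign. The documents also give neither surgical catheter timing nor its effect on success.

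Direction and size are therefore unknown. The illustration shows only that a shift of 10 points or more, if it occurred, could readily produce a significant result with equal true success. Action is worthwhile because the comparison serves a stated objective, but the study's main result does not depend on it.

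**What to change.** 1. **Section 16.6, item 6.** Drop the significance test. Report the day-3 volume-based rate for the PUL arm only. If surgical figures are wanted, give them descriptively for a labelled subset whose charts hold both volumes, with the number of charts that do not.
2. **Between-arm voiding comparison.** Use one rule both arms can meet, timed from the procedure. The 1-month catheter-free rate already planned for PUL is a natural candidate, beside items 5 and 7. State how a chart with no entry is handled and whether intermittent self-catheterisation counts. Scheduled review and chart review will still differ in completeness, so the report should say so.
3. **Sections 15.8.2 and 15.8.3.** Add the date and result of the first post-operative TWOC, voided volume and PVR where charted, and dates of catheter removal and re-insertion, including those in hospital. If the eCRF already has these fields, the protocol need only say so and give the derivation.

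The cost is a few more abstraction fields from charts already being read, some plan wording, and the loss of one nominal between-arm test. New fields cannot recover volumes that were never charted, which is why the comparison should rest on the catheter-based rule. Patient care does not change.
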